6.2. Preparation, Handling, Storage, and Accountability

The Pharmacy Manual provides information about the handling and storage of the study intervention, as well as the site responsibility and accountability for the administered products.

Additional information about the study intervention administration is provided in other documents.

Site responsibilities and accountability

1. The investigator or designee must confirm appropriate storage conditions have been maintained during transit for all study intervention received and any discrepancies are reported and resolved before use of the study intervention.
2. Only participants enrolled in the study may receive study intervention. Only authorized study personnel may supply, prepare, or administer study intervention. All study intervention must be stored in a secure, environmentally controlled, and monitored (manual or automated) area in accordance with the labeled storage conditions with access limited to the investigator and authorized study personnel.
3. The investigator or authorized study personnel are responsible for study intervention accountability, reconciliation, and record maintenance (i.e., receipt, reconciliation, and final disposition records).
4. Further guidance and information for the final disposition of unused study interventions are provided in the Pharmacy Manual.

In addition, the investigator or his/her designee is responsible for the following (see also Section 6.3):

- explaining the correct use of the investigational agent to the participant or participant's caregiver; and
- verifying those instructions are followed properly.

6.3. Measures to Minimize Bias

This is an open-label study. The site will record the intervention assignment on the applicable case report form (CRF).

6.4. Study Intervention Compliance

Every attempt will be made to select participants who have the ability to understand and comply with instructions. The investigator is responsible for discussing methods with the participants and caregiver before study entry to ensure high treatment compliance.

Throughout the study, site personnel, the participant, or the caregiver will record information about injections in the Study Intervention Administration Logs, including:

- the date, time, and anatomical location of administration of ixekizumab (for treatment compliance);
- syringe number;
- who prepared (if applicable) and administered ixekizumab; and
- the reason, if ixekizumab was not fully administered or missed.

As indicated in the SoA (Section 1.3), the Study Intervention Administration Log will be dispensed to all participants or their caregivers. Either the participant or the caregiver will complete the Log with the information about injections and bring it to the site at each regular study visit.

Participants' compliance with ixekizumab will be assessed at each regular visit. Compliance will be assessed by the number of injections needed versus the number of injections administered to the participants. Deviation(s) from the prescribed dosage regimen should be recorded in the electronic case report form (eCRF).

6.5. Dose Modification

Not applicable.

6.6. Continued Access to Study Intervention after the End of the Study

Ixekizumab will not be made available to participants at the conclusion of the study. Lilly will provide Ixekizumab from Week 0 to Week 20. Last study dose is scheduled at Week 20.

6.7. Treatment of Overdose

Refer to the IB for ixekizumab.

6.8. Concomitant Therapy

All concomitant medication taken during the study must be recorded on the Concomitant Medication CRF at the study visits indicated in the SoA (Section 1.3). Treatment with concomitant PsO and PsA therapies during the study will be permitted only as outlined in the inclusion and exclusion criteria (Sections 5.1 and 5.2, respectively) and as described in the paragraphs below. Participants taking permitted medications need to be documented to be in stable control. After trial enrollment, significant dose escalation of a concomitant medication should be discussed with Lilly medical before allowing participant to receive study intervention.

Table RHCZ.6.3 summarizes concomitant medications that are and are not permitted and their conditions for use during the study.

Table RHCZ.6.3. Concomitant Medications Permitted/Not Permitted in the Study and Conditions for Use

Drug Class	Permitted/Not Permitted during the Trial	Conditions for Use
Bath oils and oatmeal bath preparations	Permitted	Not to be used within 12 hours of a study visit.
NSAIDs, acetaminophen, or aspirin	Permitted	Allowed as needed.
Shampoos	Permitted	May not contain >3% salicylic acid, corticosteroids, coal tar, or vitamin D3 analogues. Not to be used within 12 hours of a study visit.
Topical moisturizers/emollients and other non-prescription topical products	Permitted	Do not contain urea, >3% salicylic acid, alpha- or beta-hydroxyl acids, corticosteroids, or vitamin D3 analogues. Not to be used within 12 hours of a study visit.
Topical steroids		
Mild (such as hydrocortisone)	Permitted	Permitted for use limited to the face, axilla, groin, and/or genitalia, as needed. These topical medications should not be used within approximately 24 hours before study visits requiring sPGA and PASI measures. More widespread use on large surfaces is not permitted.
Strong (such as mometasone), very strong (betamethasone) ^a , and halogenated steroids (clobetasone)	Not permitted	
Biologic agents other than study intervention as part of this protocol	Not Permitted	Washout periods before baseline (Week 0, Visit 2); at least 5 half-lives
IL-17, IL-23p19 antagonists, other than the 2 products used as part of this protocol.	Not permitted	Must have never received ixekizumab or IL-23p19 antagonists; or participated in any study investigating IL-23p19 antagonists. Participant with previous exposure to another IL-17 antagonist(s) will be limited to approximately 15% of the total participant population.
Natalizumab or other agents targeting α 4 integrin	Not permitted	Must have never received.
Phototherapy (including either oral and topical PUVA light therapy, UVB, or self-treatment with tanning beds or therapeutic sunbathing)	Not permitted	Must not have received within 4 weeks of baseline (Week 0, Visit 2).

Concomitant Medications Permitted/Not Permitted in the Study and Conditions for Use

Drug Class	Permitted/Not Permitted	Conditions for Use
Systemic nonbiologic psoriasis therapy (e.g., oral PUVA light therapy, cyclosporine, corticosteroids, MTX, oral retinoids, mycophenolate mofetil, thioguanine, hydroxyurea, sirolimus, azathioprine, fumaric acid derivatives, apremilast, and 1,25 dihydroxy vitamin D3 and analogues)	Not permitted (for PsO participants) Permitted (for PsO participants who met PsA criteria and PsA participants) with conditions	Must not have received within 4 weeks of baseline (Week 0, Visit 2). Stable dose allowed. Stable doses with no dose adjustments, changes, and/or introduction of a new csDMARD Allowed doses: 
 • Oral or parenteral MTX; 10 to 25 mg/week • Leflunomide: up to 20 mg/day • Sulfasalazine: up to 3 g/day • Cyclosporine: up to 5 mg/kg/day
Vaccine, Bacillus Calmette-Guérin	Not permitted	Must not have received within 12 months of baseline (Week 0, Visit 2). Should not receive within 12 months of completed treatment in this study.
Vaccines, live	Not permitted	Must not have received within 12 weeks of baseline (Week 0, Visit 2). Should not receive within 15 weeks of completed treatment in this study.
Vaccines, non-live seasonal and/or emergency	Permitted with conditions	Killed/inactive, RNA vaccine, or subunit vaccines are expected to be safe; however, their efficacy with concomitant ixekizumab treatments is unknown. Check with Lilly Medical Team (CRS/CRP) before administration.

Abbreviations: CRS/CRP = clinical research scientist/clinical research physician; csDMARD = conventional synthetic disease-modifying antirheumatic drug; IL = interleukin; MTX = methotrexate; NSAID = nonsteroidal anti-inflammatory drug; PASI = Psoriasis Area and Severity Index; PsA = psoriatic arthritis; PsO = plaque psoriasis; PUVA = psoralen and ultraviolet A; RNA = ribonucleic acid; sPGA = static Physician Global Assessment; UVB = ultraviolet B.

^a Mason et al. 2002.

Additional drugs are to be avoided during the study unless required to treat an AE or for the treatment of an ongoing medical problem. If the need for concomitant medication arises, the investigator should base decisions on the participant and clinical factors. Any additional medication (including the limited use of therapeutic agents which, if used under treatment regimens other than for treating an AE or for appropriate medical management, might be considered PsO/PsA therapies) whether prescription or over-the-counter, used at baseline (Week 0, Visit 2) and/or during the course of the study, must be documented with the start and stop dates on the Concomitant Medications CRF.

Participants will maintain their usual medication regimen for other concomitant diseases throughout the study unless those medications are specifically excluded in the protocol.

Participants taking concomitant medications should be on stable doses at the time of baseline (Week 0, Visit 2) and should remain at a stable dose throughout the study, unless changes need to be made for an AE or for appropriate medical management. Other medications may be allowed if approved by the Sponsor or its designee.

Participants should be instructed to consult the investigator or other appropriate study personnel at the site before taking any new medications or supplements. Any changes in medications not addressed above should be discussed by the investigator with the Sponsor.

7. Discontinuation of Study Intervention and Participant Discontinuation/Withdrawal

Discontinuation of specific sites or of the study as a whole are handled as part of Section 10.1, Section 10.1.7.

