[47] Are currently receiving treatment with any biologic or small molecule therapy for PsA or PsO, including investigational therapies (such as, but not limited to, a TNFi, IL-1 receptor antagonists, IL-6 inhibitor, anti-IL-12/23p40, T cell or B cell targeted therapies, phosphodiesterase [PDE] 4 inhibitors, or Janus kinase [JAK] inhibitors), or have received denosumab.

[48] Have received treatment with IL-17 or IL12/23 targeted Mab therapy.

[49] Have used disease-modifying antirheumatic drug (DMARDs) other than MTX, leflunomide, sulfasalazine, or hydroxychloroquine (e.g., gold salts, cyclosporine, azathioprine, dapsone, 6-mercaptopurine, mycophenolate mofetil, or any other immunosuppressive agents) in the 8 weeks prior to baseline (Week 0, Visit 2).

Have discontinued MTX or sulfasalazine within the 8 weeks prior to baseline, or hydroxychloroquine within 12 weeks prior to baseline.

If taking MTX, leflunomide, sulfasalazine, or hydroxychloroquine must have been treated for at least 12 weeks prior to baseline and on a stable dose for at least 8 weeks prior to baseline, as follows: oral or parenteral MTX = 10 to 25 mg/week; leflunomide = 20 mg/day; sulfasalazine = up to 3 g/day; or hydroxychloroquine = up to 400 mg/day. The dose of these allowed concomitant medications must remain unchanged until W12 of the study, unless changes are required for safety issues. Local standard of care should be followed for concomitant administration of folic acid with MTX.

[50] Are receiving treatment with more than 1 conventional DMARD (MTX, leflunomide, sulfasalazine, or hydroxychloroquine) at study entry.
Note: Under no circumstances will simultaneous use of MTX and leflunomide be allowed at any time during the study for safety reasons.

[51] Have discontinued leflunomide within 4 weeks prior to baseline or have received leflunomide from 4 to 12 weeks prior to baseline (Week 0, Visit 2) and have not undergone a drug elimination procedure.

[52] Use of oral corticosteroids at average daily doses of >10 mg/day of prednisone or its equivalent, or use of variable doses of any oral corticosteroids, within 4 weeks prior to baseline (Week 0, Visit 2).

- [53] Have received any parenteral glucocorticoid administered by intraarticular, intramuscular, or intravenous (IV) injection within 6 weeks prior to baseline (Week 0, Visit 2), or for whom a parenteral injection of glucocorticosteroids is anticipated until W12 of the study.

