- [54] Concomitant use of nonsteroidal anti-inflammatory drug (NSAIDs), including cyclooxygenase-2 (COX-2) inhibitors, unless the patient is on a stable dose for at least 2 weeks prior to baseline (Week 0, Visit 2).
- [55] Use of any opiate analgesic at average daily doses of >30 mg/day of morphine or its equivalent or use of variable doses of any opiate analgesic within 6 weeks prior to baseline (Week 0, Visit 2).
- [56] Have a diagnosis of other inflammatory arthritic syndromes such as rheumatoid arthritis (RA), ankylosing spondylitis, reactive arthritis, or enteropathic arthritis.
- [57] Have active Crohn's disease or active ulcerative colitis.
- [58] Have diagnosis of fibromyalgia.
- [59] Have a chronic pain condition that would confound evaluation of the patient.
- [60] Have evidence of active vasculitis or uveitis.
- [61] Have had surgical treatment of a joint within 8 weeks prior to baseline or will require such up to Week 24.

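### The NSAID row of Table RHCZ.6.3 is at odds with the general stable-dose rule in Section 6.8, so a PsA participant's background NSAID may change between Week 0 and Week 24

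*Protocol*

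**What the plan says.** The relevant text is in Protocol Section 6.8 and Section 5.2.

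- **Table RHCZ.6.3, NSAID row.** NSAIDs, acetaminophen and aspirin are permitted, and the only condition is "Allowed as needed". The row is not split by indication and sets no limit on dose or timing.
- **Section 6.8, text after the table.** Participants on concomitant medication should be on stable doses at baseline and "should remain at a stable dose throughout the study, unless changes need to be made for an AE or for appropriate medical management".
- **Section 6.8, last sentence.** "Any changes in medications not addressed above should be discussed by the investigator with the Sponsor".
- **Section 6.8, opening paragraph.** "Treatment with concomitant PsO and PsA therapies during the study will be permitted only as outlined in the inclusion and exclusion criteria"; the sentence then adds whatever the rest of the section describes. The same paragraph asks for a discussion with the sponsor's medical team if a concomitant medication is significantly escalated after enrollment.
- **Exclusion [54], PsA participants.** NSAID use, including COX-2 inhibitors, is excluded "unless the patient is on a stable dose for at least 2 weeks prior to baseline".
- **Table RHCZ.6.3, systemic nonbiologic row.** This row is split by indication. It reads "Permitted (for PsO participants who met PsA criteria and PsA participants) with conditions", and the condition is "Stable doses with no dose adjustments, changes, and/or introduction of a new csDMARD".

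**The concern.** NSAIDs are used to treat the joint symptoms of PsA. A site whose PsA participant wants to raise, stop or start a regular NSAID in mid-study finds two instructions in one section. The table row lets the change happen at will. The general rule asks for a stable dose unless there is a reason to change it.

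What is at stake is the interpretation of ACR20 at Week 24, the secondary endpoint specific to PsA. Response is judged against Week 0, the study has a single arm, and several ACR components respond to analgesic or anti-inflammatory treatment. If background NSAID use at Week 24 differs from that at Week 0, the response rate reflects ixekizumab plus that change, and no control group absorbs the difference. The primary safety objective is not affected in this way.

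**Working it through.** The protocol gives no figure on NSAID use, so there is nothing to recompute. The check is to read the provisions against each other and then establish the scope.

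**1. Row against general rule.** The row permits use as the need arises. The general rule asks for a constant dose and names two grounds for change, an adverse event and appropriate medical management. The row names no ground. There are two ways to resolve this:

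- *The row governs, as the more specific text.* The last sentence of Section 6.8 supports this, since it sends only changes not already addressed to the sponsor. A regular NSAID may then change freely after Week 0.
- *The general rule governs.* The row then misstates what PsA participants may do.

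The protocol does not choose between them.

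**2. Does exclusion [54] conflict with the row?** Not by its own wording. It covers at least 2 weeks before baseline and then ends. Other PsA criteria look forward explicitly: [46] holds the allowed doses unchanged during the study periods, [49] holds them until Week 12, and [53] looks ahead to Week 12. [54] has no such clause. Criterion [52], which excludes "use of variable doses of any oral corticosteroids, within 4 weeks prior to baseline", and criterion [55] on opiates are likewise pre-baseline windows. What [54] does is give PsA participants who take NSAIDs a stable dose at Week 0. The row does not preserve it.

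**3. How the same table treats comparable cases.** The systemic-therapy row separates the indications and fixes doses in PsA. Mild topical steroids are also allowed as needed, but not within about 24 hours of visits with sPGA and PASI. Bath oils, shampoos and emollients carry a 12-hour limit before visits. The skin endpoints are thus shielded from symptomatic treatment close to assessment. The NSAID row has no corresponding condition for the joint endpoint.

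**4. Scope, from the protocol's own numbers.**

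- PsA share of planned enrollment (Section 9.7): 100 / 250 = 40%.
- Secondary endpoints (Section 3): PASI 75, sPGA (0,1) and ACR20, so 1 of 3 is exposed.
- ACR20 (Section 8.1.2) requires at least 20% improvement in tender joints, in swollen joints, and in at least 3 of 5 core items. The patient-reported items are pain VAS, patient global VAS and HAQ-DI, which is 3 of 5. These alone could meet the core-item requirement, but both joint counts must improve as well.
- Nonresponder imputation (Section 9.3.1) covers failure to meet the response criteria, missing data, treatment discontinuation and no postbaseline observation. A change in NSAID use is not listed, so a participant whose NSAID changed is classified on the observed result.

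These figures give the reach of the point, not the size of an effect.

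**The case against.** The strongest reply is that the provisions can be read together. A row for a named drug class ordinarily prevails over a general sentence. The general sentence says only that doses should stay stable, and as-needed analgesia fits its medical-management exception without strain. The opening sentence of Section 6.8 is also satisfied, because it permits what the section goes on to describe, and the table is part of that. On this view the row is a deliberate choice, and a defensible one in a Phase 4 safety study at the approved dose.

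Much of this stands. It softens the conflict but does not remove it: as-needed use requires no reason for a change, the general rule does, and nothing says which applies. Even if the row is deliberate, it leaves the NSAID background of PsA participants open while the same table fixes their csDMARDs.

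The safeguards also count. Significant escalation is to be discussed with the sponsor, although significant is not defined. Participants are told to consult the site before taking new medication. Concomitant medication is recorded on the CRF and summarized (Section 9.4.3). Drift is therefore limited and visible, but not prevented.

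A reader might infer two stronger things. One is that the row contradicts exclusion [54]. It does not, because [54] ends at baseline. The other is that ACR20 will be inflated. The documents do not support that either: NSAID use could rise or fall after Week 0, and no data on it are given.

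**Conclusion.** The point holds as a minor inconsistency within Section 6.8, with a cheap improvement available. The as-needed row and the stable-dose rule give different instructions for NSAIDs, and the row does not keep the stable background that [54] establishes for PsA participants.

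The consequence is possible confounding, of unknown size and direction, of one secondary endpoint in about 100 planned participants. No shift in the ACR20 rate can be estimated from the protocol. The effect is bounded in kind by the swollen-joint requirement, the escalation discussion and CRF recording. No hypothesis test depends on it (Section 9.1), and the primary objective is safety.

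The conclusion assumes that some PsA participants will take regular NSAIDs. Exclusion [54] anticipates this, but the protocol does not quantify it.

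**What to change.** Split the NSAID row of Table RHCZ.6.3 by indication, as the systemic-therapy row already is:

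- **PsO participants without active PsA:** keep as-needed use.
- **PsA participants:** regular NSAIDs, including COX-2 inhibitors, stay at the baseline dose through Week 24 unless a change is needed for an adverse event or appropriate medical management. Any change is recorded on the Concomitant Medications CRF. Acetaminophen and low-dose aspirin remain allowed.

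This aligns the row with the general rule and makes a stable dose the default. It does not rule out every change, since the medical exceptions remain, but a change then needs a reason and is documented.

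The cost is one amended table row and a short note to sites. No new data are collected. The downside is slightly less freedom to adjust analgesia in PsA participants.

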- [42] Have received systemic non-biologic PsO therapy (including, but not limited to, oral psoralens and ultraviolet A [PUVA] light therapy; cyclosporine; corticosteroids; methotrexate [MTX]; oral retinoids; mycophenolate mofetil; thioguanine; hydroxyurea; sirolimus; azathioprine; fumaric acid derivatives; or 1,25 dihydroxy vitamin D3 and analogues) or phototherapy (including either oral and topical PUVA light therapy, ultraviolet B [UVB] or self-treatment with tanning beds or therapeutic sunbathing) within 4 weeks prior to baseline (Week 0; Visit 2); or had topical PsO treatment (including, but not limited to, corticosteroids, anthralin, calcipotriene, topical vitamin D derivatives, retinoids, tazarotene, emollients and other non-prescription topical products containing urea, >3% salicylic acid, or alpha- or beta-hydroxyl acids, and medicated shampoos [e.g., those that contain >3% salicylic acid, corticosteroids, coal tar, or vitamin D3 analogues]) within the previous 2 weeks prior to baseline (Week 0; Visit 2).

Exceptions: class 6 (mild, such as desonide) or class 7 (least potent, such as hydrocortisone) topical steroids will be permitted for use limited to the face, axilla, and/or genitalia.

- [43] Have pustular, erythrodermic, and/or guttate forms of PsO.
- [44] Had a clinically significant flare of PsO during the 12 weeks prior to baseline (Week 0; Visit 2).
- [45] Have allergy to rubber or latex.

PsA Participants

- [46] Have used conventional synthetic disease-modifying antirheumatic drug (csDMARDs) other than MTX, leflunomide, sulfasalazine, or cyclosporine in the 8 weeks prior to baseline (Week 0; Visit 2).

Have discontinued MTX, sulfasalazine, or cyclosporine within 12 weeks prior to baseline (Week 0; Visit 2).

If taking MTX, leflunomide, sulfasalazine, or cyclosporine, must have been treated for at least 12 weeks prior to baseline *and* on a stable dose for at least 8 weeks prior to baseline, as follows: oral or parenteral MTX = 10 to 25 mg/week; leflunomide = 20 mg/day; sulfasalazine = up to 3 g/day; or cyclosporine up to 5 mg/kg/day. The dose of these allowed concomitant medications must remain unchanged during the study periods of the unless changes are required for safety issues. Local standard of care should be followed for concomitant administration of folic acid with MTX.

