8.1.1. Efficacy Assessments

8.1.1.1. Psoriasis Area and Severity Index (PASI 75, PASI 90, PASI 100)

The PASI will be used to assess PsO and PsA. The PASI combines assessments of the extent of body-surface involvement in 4 anatomical regions (head, trunk, arms, and legs) and the severity of desquamation (scaling), erythema, and plaque induration/ infiltration (thickness) in each region, yielding an overall score from 0 for no psoriasis up to 72 for the most severe disease (Fredriksson and Pettersson 1978). The PASI has been the most frequently used endpoint and measure of psoriasis severity in clinical trials (EMA 2004; Menter et al. 2008). A clinically meaningful response is a PASI 75, which represents at least a 75% decrease (improvement) from the baseline PASI score. As minimum treatment response, the European and German guidelines mention a PASI 50 response. Higher levels of clearance (PASI 90), as well as complete resolution of psoriasis (PASI 100), have become additional endpoints because of the increasing recognition of the association of higher clearance with greater health-related quality of life (Puig 2015).

Participants achieving PASI 75, 90, or 100 are defined as having an improvement of at least 75%, 90%, or 100%, respectively, in the PASI, compared to baseline.

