9.5.3 Secondary Endpoint(s) Analysis

Endpoints Specific to Psoriasis (PsO) and Psoriatic Arthritis (PsA) Participants with 3% or More BSA of PsO

As a part of the secondary analyses, the following endpoints will be summarized (i) for the PsO indication and will be based on the PsO with no active PsA – mITT population, and (ii) for the active PsA indication and will be based on the active PsA – mITT population with BSA of PsO $\geq 3\%$ at baseline, unless otherwise specified:

Proportion of Participants with sPGA (0 or 1)

The proportion of participants achieving sPGA response of 0 or 1 at Week 12 will be summarized and the associated 95% confidence interval (CI) will be provided using normal approximation. Missing data will be imputed using the NRI method as defined in Section 9.3.1. Further details will be provided in SAP.

Proportion of Participants with PASI 75

The proportion of participants achieving a PASI 75 response at Week 12 will be summarized and the associated 95% CI will be provided using normal approximation. Missing data will be imputed using the NRI method as defined in Section 9.3.1. Further details will be provided in SAP.

Endpoints Specific to Psoriatic Arthritis (PsA)

As a part of the secondary analyses, the following endpoint will be summarized for the PsA indication and will be based on the active PsA-mITT population:

Percentage of Participants Achieving ACR20

The proportion of participants achieving a response of ACR20 at Week 24 (Visit 15) will be summarized and 95% CI will be provided using normal approximation. Further details will be provided in SAP.

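### PsA participants have no pre-baseline washout for the strong topical steroids that the trial bars, so their Week 0 PASI may be taken too soon after stopping one

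*Protocol*

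**What the plan says.** In Table RHCZ.6.3 (Section 6.8) the row for "Strong (such as mometasone), very strong (betamethasone) ^a , and halogenated steroids (clobetasone") is marked as not permitted, and its conditions column is empty. The row for mild topical steroids allows limited use and adds: "These topical medications should not be used within approximately 24 hours before study visits requiring sPGA and PASI measures".

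Exclusion [42] (Section 5.2) bars topical psoriasis treatment, corticosteroids included, "within the previous 2 weeks prior to baseline (Week 0; Visit 2"). It excepts class 6 and 7 steroids on the face, axilla and genitalia. It stands under the heading for PsO participants. Among the criteria for PsA participants, [52] and [53] restrict oral and parenteral corticosteroids. Neither the PsA criteria [46] to [61] nor the general criteria [12] to [41] mention topical treatment.

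Section 6.8 also says: "Participants taking concomitant medications should be on stable doses at the time of baseline (Week 0, Visit 2").

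Screening lasts 5 to 28 days (Section 4.1.1). Efficacy baseline is the last value on or before the first injection, usually Week 0 (Section 9.5.1). PASI 75 "represents at least a 75% decrease (improvement) from the baseline PASI score" (Section 8.1.1.1). Section 9.5.3 summarizes Week 12 PASI 75 and sPGA (0,1) for PsO participants without active PsA and, separately, "for the active PsA indication and will be based on the active PsA" mITT population with BSA of at least 3% at baseline.

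**The concern.** PASI 75 is a ratio to the participant's own Week 0 score, so whatever shifts that score shifts the hurdle. A strong topical steroid has to stop for the trial, but for these PsA participants nothing says how long before Week 0. The score may then be taken while the steroid still suppresses the plaques, or while they flare after its withdrawal. The proper reference is the same participant's settled score on permitted stable background treatment.

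The PsO group is reported on the same endpoint with a 14-day minimum. The two PASI 75 summaries in Section 9.5.3 therefore rest on baselines taken under different rules.

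**Working it through.** **1. Does any other rule supply the washout?**

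- Exclusion [42] cannot be stretched to PsA participants. It also bars methotrexate and cyclosporine in the 4 weeks before baseline. Exclusion [46] allows both at stable doses in PsA participants, and the systemic non-biologic row of Table RHCZ.6.3 reads "Permitted (for PsO participants who met PsA criteria and PsA participants) with conditions".
- A PsA participant who falls short of BSA 10%, sPGA 3 or PASI 12 does not meet inclusion [6] and [7], so does not enter as a PsO participant.
- The 24-hour limit covers mild steroids only.
- The stable-dose sentence sets no interval for a drug that must stop.

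No rule closes the gap.

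**2. How short can the interval be?**

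The table governs use during the trial and does not say when that begins.

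- Ban starts at Visit 1: the minimum is the shortest screening period, 5 days.
- Ban starts at first dose: the minimum is 0 days.
- PsO participants under [42]: 14 days.

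On the Visit 1 reading, permitted screening lengths are 5 to 28 days, which is 28 − 5 + 1 = 24 values. Those under 14 days are 5 to 13, which is 9 values, falling short by 9 down to 1 days. The other 15 values give 14 days or more. These count permitted values; they do not forecast actual screening times.

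**3. What would a shifted baseline do to PASI 75?**

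Let r be the fraction by which Week 0 PASI lies below the participant's settled score. Positive r means residual steroid effect, negative r means rebound. The fall needed from the settled score is 1 − 0.25 × (1 − r). The documents give no value for r, so −0.2 to +0.2 is an assumption.

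| r (assumed) | Fall needed |
|---|---|
| −0.2 | 1 − 0.25 × 1.2 = 70% |
| −0.1 | 1 − 0.25 × 1.1 = 72.5% |
| 0 | 75% |
| +0.1 | 1 − 0.25 × 0.9 = 77.5% |
| +0.2 | 1 − 0.25 × 0.8 = 80% |

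**4. How does that compare with the precision of the summary?**

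About 100 PsA participants are planned (Section 9.7); the size of the subgroup with BSA of at least 3% is not given. Assume n = 30 or 60 and an 80% response.

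- One responder gained or lost: 1/30 = 3.3 points, or 1/60 = 1.7 points.
- 95% CI half-width by normal approximation, 1.96 × √(0.8 × 0.2 / n): 14.3 points at n = 30, 10.1 points at n = 60.

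A few misclassified participants would stay within the reported uncertainty.

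**5. What else is touched?**

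sPGA (0,1) is an absolute score, so it is affected at most through who has BSA of at least 3% at baseline. The primary safety analysis uses no PASI value.

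**The case against.** The best case against the point is that it is narrow. It needs active PsA, BSA of at least 3%, skin disease below the moderate-to-severe criteria, use of a strong topical steroid, and a first dose within 14 days of stopping it. The PASI 75 objective in Section 3 is labelled as specific to the psoriasis group, where [42] applies. No hypothesis is tested (Section 9.1). Medications used at baseline or during the study need start and stop dates, so participants who stopped during screening can be identified. All of this stands and limits the weight of the point. Recorded dates do not, however, restore an undisturbed baseline.

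Three stronger readings are tempting, and the documents do not support them.

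- A reader might infer that PASI 75 is understated. That follows only from residual suppression; rebound would lower the hurdle and overstate it. Nothing in the protocol says which prevails.
- A reader might take 5 days as the protocol's minimum. It holds only if the ban starts at Visit 1, which is not stated.
- A reader might see a drafting slip because the seven other barred classes carry a pre-baseline condition, as phototherapy does: "Must not have received within 4 weeks of baseline (Week 0, Visit 2"). But none of the topical rows repeats a washout, so this row follows its neighbours. Nothing marks a redaction in the empty cell, although an entry lost when the table was converted to text cannot be excluded. The point rests on [42] being confined to PsO participants, not on that contrast.

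It is also fair to say that medicated shampoos and some non-prescription topical products are barred during the trial with no interval for PsA participants. The fix below leaves those as they are.

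**Conclusion.** The gap is real and minor. For active PsA participants below the moderate-to-severe PsO criteria, the protocol sets no minimum time off a strong, very strong or halogenated topical steroid before the Week 0 PASI, although it requires 2 weeks of PsO participants. The Week 12 PASI 75 proportion in Section 9.5.3(ii) may be distorted in either direction.

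The size cannot be derived, because the share of users, the subgroup size and the residual or rebound effect are all absent from the document. Under the assumptions shown, the hurdle for an affected participant moves by at most 5 percentage points either way, and the effect on the proportion is probably modest against a half-width of 10 to 14 points. The endpoint is secondary and descriptive.

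**What to change.** In the Table RHCZ.6.3 row for strong, very strong and halogenated topical steroids, state that they must not be used in the 2 weeks before baseline (Week 0, Visit 2). Apply this to all participants, including every PsA participant whatever the BSA at screening. Keep the mild-steroid exception.

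The rule should not be tied to screening BSA. The Section 9.5.3(ii) subgroup is defined at baseline, so a participant held below 3% by the steroid at Visit 1 could rise above it afterwards and escape the rule. Footnote g of the Schedule of Activities also leaves it unclear whether PsA participants have a BSA at Visit 1.

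The change is one sentence. Its cost falls on PsA participants using such a steroid at Visit 1: a screening period of at least 14 days instead of 5, so up to 14 − 5 = 9 extra days, within the 28-day window. PsO participants already meet the interval under [42].
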